#### Analyses of ppFEV1 at Additional Timepoints

The above approach will be repeated for testing treatment differences from placebo in the other timepoints, with a two-sided significance level of 0.05:

- Change from baseline in ppFEV1 at visit 3 (week 1)
- Change from baseline in ppFEV1 at visit 4 (week 2).

#### Mixed Model for Repeated Measures

The change from baseline in ppFEV1 at each visit (week 1, 2, and 4) will also be evaluated using a mixed effect model for repeated measure (MMRM).

For Cohort 1, to evaluate treatment differences of ppFEV1 change from baseline across time points (week 1, 2 and 4), a likelihood-based mixed effect model repeated measures (MMRM) analysis will be run on ITT analysis set. The model will include the change from baseline in ppFEV1 as the dependent variable; the treatment, visit and treatment by visit interaction term will be treated as fixed effects, and covariates of baseline lung function category (ppFEV1 40.0% to 55.0% or 55.1% to 80.0% for Cohort 1). Subject will be treated as a random effect.

For Cohort 2, the MMRM analysis will be performed for the change from baseline in ppFEV1 to estimate the treatment difference at Week 4. The model will include all participants in the ITT population, and the dependent variable will be the observed change from baseline in ppFEV1 at each post-randomization visit. Covariates in the model will include the fixed categorical effects of treatment, concomitant use of hypertonic saline, visit and treatment by visit interaction, as well as the continuous fixed covariates of baseline ppFEV1 and baseline ppFEV1 by visit interaction.

Sponsor: SPYRYX Biosciences

Protocol no: SPX-101-CF-201

Descriptive statistics will be presented for Visit 5 (week 4), and for all visits for Cohort 2, and will include number of observations, unadjusted mean, standard deviation, median, first quartile, third quartile, minimum and maximum, and adjusted mean from the mixed model. Treatment differences from placebo will be presented and estimated via least squares means from the analysis model along with 95% confidence intervals. The 2-sided p-value of the overall analysis at Week 4 will be presented. These models will be performed using an unstructured correlation matrix to model the within-subject errors and the Kenward-Rogers correction to degrees of freedom will be applied. If the unstructured covariance matrix does not converge when fitting the mixed model, further investigation into the most appropriate correlation matrix will be conducted. The final selection of the correlation matrix to be used in fitting the mixed model will be noted in the footnote and fully documented in the results section of the clinical study report.

#### ANCOVA with Multiple Imputation of ppFEV1

Multiple imputation will be used to explore the effect of missing data on the primary endpoint in Cohort 2 only. All missing ppFEV1 data at baseline and Visit 5 (week 4) will be imputed for all enrolled subjects, utilizing the full conditional specification method (FCS). Missing values will be imputed using treatment, hypertonic saline use, sex, age group, and the ppFEV1 recorded at each time point (including baseline). For this analysis, CFB will be calculated for all subjects following imputation.

An ANCOVA model with treatment as a factor, and concomitant use of hypertonic saline and baseline ppFEV1 as covariates, will be run on the imputed data from PROC MI and results will be combined using PROC MIANALYZE. Further details of the multiple imputation are described in section 12.6.5.

Descriptive statistics of the imputed data combined with observed data will include the number of observations, unadjusted mean, standard deviation, median, first quartile, third quartile, minimum and maximum, and least squares mean. Treatment differences from placebo will be presented and estimated by least squares means from the analysis model along with 95% confidence intervals and associated 2-sided p-value.

#### **12.6.2 Secondary Variables**

##### FEV1

Similar ANCOVA analyses as the primary analysis, using a two-sided significance level of 0.05, will be repeated for testing treatment differences from placebo in the endpoints:

- Change from baseline in FEV1 at visit 3 (week 1)
- Change from baseline in FEV1 visit 4 (week 2)
- Change from baseline in FEV1 visit 5 (week 4)

##### FVC and ppFVC

Similar ANCOVA analyses as the primary analysis, using a two-sided significance level of 0.05, will be repeated for testing group differences in the endpoints:

- Change from baseline in FVC at visit 3 (week 1)
- Change from baseline in FVC at visit 4 (week 2)
- Change from baseline in FVC at visit 5 (week 4)
- Change from baseline in ppFVC at visit 3 (week 1)
- Change from baseline in ppFVC at visit 4 (week 2)
- Change from baseline in ppFVC at visit 5 (week 4)

#### FEF25-75

Similar ANCOVA analyses as the primary analysis, using a two-sided significance level of 0.05, will be repeated for testing group differences in the endpoints:

- Change from baseline in FEF25-75 at visit 3 (week 1)
- Change from baseline in FEF25-75 at visit 4 (week 2)
- Change from baseline in FEF25-75 at visit 5 (week 4)

#### Cystic Fibrosis Questionnaire – Revised (CFQ-R)

The respiratory and physical domain scores will be calculated as described in Section 8. The observed scores at Visit 1, Visit 5 (week 4), and change-from baseline at Visit 5 (week 4) will be summarized for each domain. Scores from the respiratory and physical domains will be listed.

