**STATISTICAL METHODS:**

**Efficacy Analysis**

The primary endpoint is the change from baseline in ppFEV1 at Week 4 (Day 29).

The change from baseline in ppFEV1 at Week 4 will be summarized and compared between each treatment group and placebo. The primary analysis will be based on an analysis of covariance (ANCOVA), incorporating the categorical stratification variable of baseline lung function in Cohort 1, and the stratification variable of concomitant hypertonic saline use in Cohort 2.

Similar analysis will be performed for the change from baseline in ppFEV1 (Weeks 1 and 2), FEV1, ppFVC, and FVC at each visit (Week 1, 2, and 4).

The change from baseline in ppFEV1 at each visit (week 1, 2, and 4) will also be considered based on a mixed effect model for repeated measure (MMRM).

The change from baseline in CFQ-R respiratory domain score and physical domain score at Week 4 will be summarized and compared between each treatment group and placebo.

The number and percentage of subjects with pulmonary exacerbation will be summarized.

The effect of regular use of concomitant hypertonic saline will be explored across the primary and secondary endpoints.

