##### CFQ-R

The change from baseline in CFQ-R respiratory domain and physical domain at Week 4 will be summarized and compared between the treatment groups and the placebo.

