## 7.2 Secondary Efficacy Variables

- Change from baseline in ppFEV1 at visits 3 and 4 (weeks 1 and 2)
- Change from baseline in FEV1 at visits 3, 4 and 5
- Change from baseline in forced vital capacity (FVC) and percent predicted FVC (ppFVC) at visits 3, 4 and 5
- Change from baseline in 25-75% forced expiratory Flow (FEF25-75) at visits 3, 4 and 5
- Change from baseline in Cystic Fibrosis Questionnaire-Revised (CFQ-R) (respiratory and physical domains) at visit 5.

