### 12.6.1 Primary Variable

#### Primary Efficacy Analysis

The primary efficacy endpoint is the change from baseline in ppFEV1 at visit 5 (week 4). The change from baseline in ppFEV1 at each visit (Weeks 1, 2, and 4) will be summarized and compared between each treatment group and placebo. No imputation of missing data will be done for this analysis.

The comparison between each treatment group and placebo will be evaluated by using an analysis of covariance (ANCOVA) model, which will include treatment as the factor, and the stratification factor as a covariate (i.e., baseline lung function categories [ppFEV1 40.0% to 55.0% or 55.1% to 80.0% for Cohort 1] and the concomitant use of hypertonic saline for Cohort 2). Also included in the ANCOVA model for Cohort 2 is baseline ppFEV1. Descriptive statistics will include the number of observations, unadjusted mean, standard deviation, median, first quartile, third quartile, minimum and maximum, and least squares mean. Treatment differences from placebo will be presented and estimated by least squares means from the analysis model along with 95% confidence intervals and associated 2-sided p-values, which are presented for descriptive purposes.

Sponsor: SPYRYX Biosciences

Protocol no: SPX-101-CF-201

---

As described in the power and sample size calculations in Section 6.1, Cohort 1 will be evaluated for success using a two-sided 0.15 significance level. Cohort 2 will be evaluated for success using a one-sided (upper) 0.10 significance level. For Cohort 2, both the one-sided p-value and the lower bound (i.e. one-sided 90% confidence interval) will be presented.

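### The SAP gives no model or treatment difference for the two CFQ-R secondary endpoints, although the protocol says their Week 4 change will be compared with placebo

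*SAP*

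**What the plan says.** **Protocol.** CFQ-R change from baseline is a secondary efficacy variable (Section 9.6.1.1). The synopsis says that the change in "CFQ-R respiratory domain score and physical domain score at Week 4 will be summarized and compared between each treatment group and placebo". Section 13.6.4.2 repeats that the Week 4 change in the two domains "will be summarized and compared between the treatment groups and the placebo". Neither place names a model. Section 13.3 leaves the detailed methods to the SAP.

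**SAP.** Section 7.2 keeps the endpoint as secondary, for the "respiratory and physical domains) at visit 5". The analysis text in Section 12.6.2 reads: "The observed scores at Visit 1, Visit 5 (week 4), and change-from baseline at Visit 5 (week 4) will be summarized for each domain". The only other instruction in that paragraph is to list the scores.

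The spirometry endpoints are treated differently:

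- ppFEV1 at Weeks 1 and 2 (Section 12.6.1): "The above approach will be repeated for testing treatment differences from placebo in the other timepoints".
- FEV1 (Section 12.6.2): ANCOVA as for the primary endpoint "will be repeated for testing treatment differences from placebo in the endpoints".
- FVC, ppFVC and FEF25-75 (Section 12.6.2): the same ANCOVA "will be repeated for testing group differences in the endpoints".

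The primary ANCOVA that these refer to is one "which will include treatment as the factor, and the stratification factor as a covariate". For Cohort 2 it also includes baseline ppFEV1.

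**The concern.** The protocol commits to two things for CFQ-R, a summary and a comparison with placebo. The SAP carries over only the summary. CFQ-R is the trial's only patient-reported efficacy endpoint, so an analyst who follows the SAP to the letter would report no estimated effect on how patients feel or function.

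The protocol names no CFQ-R model, so the SAP is where it had to be chosen. If it is not fixed before Cohort 2 is locked and unblinded, the decision to adjust for hypertonic saline stratum, for baseline domain score, for both or for neither can be made with the results in view. SAP 4.1 (Changes from Protocol) does not record that the comparison was dropped. That section is not a complete log of differences, so its silence is a minor point.

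**Working it through.** The plan gives no CFQ-R figure to reproduce. The check has four parts: whether any SAP text supplies the comparison, how many endpoints lack one, how many subjects could contribute, and whether the stated visit is right.

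**1. Does any other SAP section fill the gap?**

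| SAP section | What it fixes for CFQ-R | Model or treatment difference? |
|---|---|---|
| 7.2 | Two domains, Visit 5, secondary status | No |
| 8.0, Change from Baseline | Both values needed; missing changes excluded | No |
| 8.0, CFQ-R Domain Scores | Scoring and item imputation | No |
| 12.0 | Default two-sided alpha of 0.05; descriptive summaries by arm and overall | No |
| 12.6 | ITT analysis set | No |
| 12.6.2, CFQ-R | Summary and listing | No |
| 12.6.4 | Hypertonic saline subgroups for ppFEV1, FEV1, FVC and ppFVC only | No |

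The sentences that extend the primary ANCOVA to other endpoints each name their endpoints, and all of those are spirometric. What is missing is therefore specific: the model, and the reported difference with its interval.

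**2. How many secondary comparisons have a stated method?**

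| Endpoint in SAP 7.2 | Comparisons | With a stated method |
|---|---|---|
| ppFEV1, Weeks 1 and 2 | 2 | 2 |
| FEV1, three visits | 3 | 3 |
| FVC, three visits | 3 | 3 |
| ppFVC, three visits | 3 | 3 |
| FEF25-75, three visits | 3 | 3 |
| CFQ-R, two domains at one visit | 2 | 0 |
| **Total** | **16** | **14** |

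14/16 = 87.5% have a method and 2/16 = 12.5% do not. FEF25-75 is not in the protocol's list of efficacy variables, yet it receives an ANCOVA. CFQ-R is in that list and does not.

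**3. How many subjects could contribute?** CFQ-R is not given to subjects who stop early (Protocol Table 2, footnote f, and Section 10.6). In Cohort 1, 46 subjects were randomized (synopsis) and 40 completed (Section 7.3.2): 40/46 = 0.870. If Cohort 2 completes at the same rate (an assumption), 45 × 40/46 = 39.1, so about 39 subjects would have a Week 4 score and about 6 would not. Using the 45 treated subjects as denominator gives 40/45 = 0.889, or about 40 with and 5 without. These figures do not measure the omission. They show why the analysed numbers should be reported by arm.

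The documents give no CFQ-R standard deviation, so precision in score points cannot be calculated. In SD units, with all 45 observed (30 versus 15), the standard error of an unadjusted difference is √(1/30 + 1/15) = 0.316 SD. The 95% CI half-width (t, 43 df) is about 0.64 SD.

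**4. Is the stated visit right?** SAP 12.6.2 summarizes scores at Visit 1. Protocol 11.1 and the schedules in both documents collect CFQ-R only at Visits 2 and 5, so a Visit 1 column would be empty. This is a clerical slip.

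**The case against.** The strongest reply is that the contradiction is softer than it looks. For spirometry the protocol names ANCOVA. For CFQ-R it asks only for a comparison, and summaries tabulated by arm place active and placebo side by side. A reader could take n, mean and SD from each arm and form a crude difference, and from the same figures a crude interval. The table shells, which are a separate document according to SAP Appendix 2, might also contain a comparison.

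Part of this stands. The shells were not available, so the finding is that the SAP text states no comparison, not that none will ever be reported. A reader could also reconstruct an unadjusted difference. But that is not a planned estimate, it cannot be adjusted for stratum or baseline score, and the protocol lists comparing as a separate act from summarizing. A table shell shows layout; the model belongs in the SAP.

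A second reply is that little depends on this. It is a Phase II secondary endpoint with no success rule and no multiplicity control (SAP 12.6.6). That is true and limits the weight of the point. It applies equally to the 14 spirometry comparisons, which do have a stated method.

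A third reply is that any particular CFQ-R model is a preference, since the protocol names none. The hypertonic saline term is not arbitrary, however. It is the Cohort 2 stratification factor, and Protocol 13.6.4.3 asks, under exploratory analyses, for every primary and secondary endpoint to be analysed accounting for hypertonic saline use. It is fair to add that SAP 12.6.1 attaches distributional checks and a rank-test fallback to the primary ANCOVA, so a CFQ-R analysis modelled on it should say whether they apply.

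**Conclusion.** The concern holds. The SAP drops a comparison that the protocol promises twice, for 2 of 16 secondary comparisons, and no other SAP section restores it. The comparator, timepoint, scoring, change-from-baseline rule, analysis set and default alpha are already fixed. Only the model and the reported difference with its interval are absent.

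This should be corrected, but it does not threaten the trial's main conclusion. The primary analysis and its success rule are untouched, and any CFQ-R comparison would be descriptive. The verdict rests on the SAP text, with the table shells not seen. The estimate of about 39 of 45 subjects with a Week 4 score assumes that Cohort 2 completes at the Cohort 1 rate.

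**What to change.** Limit the change to Cohort 2, because Cohort 1 was already analysed under SAP Version 1. Add to SAP 12.6.2:

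> Change from baseline to Week 4 in each CFQ-R domain will be compared between SPX-101 120 mg BID and placebo by ANCOVA with treatment, hypertonic saline stratum and baseline domain score, reporting the LS-mean difference, 95% CI and a descriptive two-sided p-value. The analysis uses subjects with baseline and Week 4 CFQ-R scores; the numbers with and without a Week 4 score will be shown by arm.

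This follows the Cohort 2 primary ANCOVA, with the baseline domain score in place of baseline ppFEV1. State in the same paragraph whether the assumption checks and rank-test fallback of SAP 12.6.1 apply. Change Visit 1 to Visit 2 (baseline). If the sponsor intends CFQ-R to be summarized only, SAP 4.1 should record that as a change from the protocol, with the reason.

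The cost is SAP wording and one added table from data already collected. Visits, questionnaires and sample size do not change.

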#### **12.6.3 Exploratory Analyses**

##### Pulmonary Exacerbation

The number and percentage of subjects with pulmonary exacerbation will be tabulated using the ITT analysis set, by treatment groups and total and by visit. A subject listing will be provided. Further analysis may be explored.

##### Concomitant Hypertonic Saline

The number and percentage of subjects using concomitant hypertonic saline will be tabulated using the ITT analysis set, by treatment groups and total. A subject listing will be provided. Further analysis may be explored.

#### **12.6.4 Additional Analyses**

##### Others

The change from baseline in the ppFEV1, FEV1, FVC, and ppFVC (at Weeks 1, 2 and 4, as described for the primary efficacy analysis) will be summarized and analyzed separately by subgroup (using concomitant hypertonic saline vs no concomitant hypertonic saline usage), utilizing the ITT analysis set.

Sponsor: SPYRYX Biosciences

Protocol no: SPX-101-CF-201

---

The change from baseline in ppFEV1 by strata (baseline ppFEV1  $\leq$  55%, baseline ppFEV1  $>$  55%) will be explored by treatment groups and by visit, also by combined active group and placebo group (Cohort 1 only).

The change from baseline in ppFEV1 by treatment groups, by visit and by category ( $\leq$  -10%,  $>$  -10% -  $\leq$  -5%,  $>$  -5% -  $\leq$  0%,  $>$  0% -  $\leq$  5%,  $>$  5% -  $\leq$  10%,  $>$  10% -  $\leq$  15%,  $>$  15%) will be explored.

The change from baseline in the ppFEV1, FEV1, FVC, and ppFVC (at Weeks 1, 2 and 4, as described for the primary efficacy analysis) may be summarized and analyzed separately by subgroup (CFTR Modulator Response vs No Response), utilizing the ITT analysis set. This will be done only if there is a sufficient sample size to warrant this analysis. This population cannot be defined programmatically, therefore the sponsor will review the genetic mutations for each subject, and will identify those that have class 1 or other CFTR modulator non-responsive mutations, and will provide this information to PRA.

The change from baseline in the ppFEV1 (at Weeks 1, 2 and 4, as described for the primary efficacy analysis) will be summarized and analyzed separately by subgroup based on starting a new cycle of concomitant inhaled antibiotics within +/- 3 days of start of study drug vs not starting a new cycle of inhaled antibiotics within +/- 3 days of start of study drug use in the ITT analysis set. The first data set will include patients taking inhaled antibiotics defined as those who start a cycle of inhaled antibiotics with study drug (patients who are on an on-month of an alternating month on/month off cycle with a single inhaled antibiotic and those that alternate monthly between 2 inhaled antibiotics). The second data set will include all the patients that do not begin a new inhaled antibiotic with study drug (patients who are off-cycle of an alternating month on/month off cycle, patients who are taking continuous inhaled antibiotics, or patients who are not taking inhaled antibiotics. Due to data capture limitations, these populations cannot be defined programmatically with certainty. Therefore, the sponsor will review the inhaled antibiotic usage and will identify the patients to be included in each data set.

The change from baseline in the ppFEV1 (at Weeks 1, 2 and 4, as described for the primary efficacy analysis) will be summarized and analyzed separately by subgroup (using dornase alfa and not using dornase alfa), utilizing the ITT analysis set.

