### **9.5.7 Prior and Concomitant Therapy**

Any treatment not explicitly excluded and considered necessary for the subject's welfare may be given during the study at the discretion of the Investigator. Administration of concomitant medications must be reported in the appropriate eCRF with dosage information, dates of administration, and reasons for use. Generic names for concomitant medication should be used if possible. The total daily dose should be filled in whenever possible.

Randomization (Day 1) and initiation of study drug should be scheduled to coincide with the first day of a cycle of inhaled antibiotics, if applicable. If simultaneous initiation of the study drug and inhaled antibiotics cannot be accommodated, the subject may be randomized, provided they start their 28-day cycle within  $\pm$  3 days of Visit 2.

In general, the subject's usual routine of medication and chest physiotherapy are to be continued unchanged throughout the study. The study drug should be added into the subject's treatment regimen as the last mucolytic therapy inhaled (ie, after inhalation of dornase alfa, mannitol, and/or hypertonic saline) but before the inhalation of antibiotics or corticosteroids. The only exception to this rule is on the mornings of all clinic visits. The following procedures should be followed on clinic days only:

- If a long-acting  $\beta$ -agonist (LABA) is taken regularly in the morning, instruct the subject to take it the evening prior to all clinic visits and not take it the morning until after all clinic assessments have been completed.
- If a short-acting  $\beta$ -agonist (SABA) is taken regularly, the subject should ensure that it is taken at least 4 hours before the clinic visit.
- The subject should be instructed not to take the morning dose of the study drug, but they should complete the regular routine of medications and chest physiotherapy at home (including inhaled antibiotics); the study drug will be administered during the clinic visit.

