### **13.2 Sample Size Estimation**

The study was planned for a minimum of 39 subjects per cohort to be enrolled. In Cohort 1, 46 subjects were randomized in a 1:1:1 ratio to one of the two treatment groups or placebo. The sample size of 39 subjects was chosen to provide 70% power for the Analysis of Variance (ANOVA) to detect a difference range of 4.5% to 6% in the change from baseline in ppFEV1 and FEV1 between the 2 treatment groups versus placebo, with the alpha level of 0.15 assuming a common standard deviation of 7%. The attrition rate is expected to be minimal given the 4 weeks' treatment duration.

In Cohort 2, a total of 45 subjects will be randomized in a 2:1 ratio to SPX-101 120 mg BID or placebo. The sample size of 45 subjects will provide 88% to 97% power to detect a difference range of 6% to 8% in the change from baseline in ppFEV1 between the treatment group versus placebo, with the 1-sided alpha level of 0.1 assuming a common standard deviation of 7.58%.

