#### Concomitant Hypertonic Saline

For Cohort 1, concomitant hypertonic saline use will be identified by a review of all concomitant medication terms by ATC, preferred name, and verbatim term. The Medical Monitor or designee will review all concomitant medications (while blinded to treatment information) prior to database lock, and identify which medications are inhaled hypertonic saline. This information will be recorded on a spreadsheet, finalized prior to database lock, and incorporated into analysis datasets for use in summaries and analyses.

For Cohort 2, concomitant hypertonic saline use will be identified prior to randomization by the investigator or designee and will be entered into the Interactive Voice/Web Response System.

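### The only outcome analysis by inhaled-antibiotic cycle rests on sponsor-assigned lists with no stated blinding or pre-lock rule, and its two sets mix different antibiotic transitions

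*SAP*

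**What the plan says.** **Timing.** Protocol 9.5.7 says that randomization and the first dose "should be scheduled to coincide with the first day of a cycle of inhaled antibiotics", where this applies. If that cannot be arranged, a subject may still be randomized provided the 28-day cycle starts within 3 days either side of Visit 2. The 3- to 28-day screening period exists to make this possible (Protocol 10.1; SAP 6.0).

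**Models.** Cohort 2 is stratified by hypertonic saline use only (Protocol 13.4; SAP 6.2). Besides treatment, the primary ANCOVA contains "the concomitant use of hypertonic saline for Cohort 2). Also included in the ANCOVA model for Cohort 2 is baseline" ppFEV1 (SAP 12.6.1). The MMRM and the multiple-imputation analysis have no antibiotic term either. SAP 12.2 counts Cohort 2 subjects taking inhaled antibiotics but does not separate cycle starters.

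**The antibiotic analysis.** SAP 12.6.4 repeats the ppFEV1 analysis in two sets. Set 1 holds subjects who begin a cycle with study drug: month-on/month-off users entering an on month, and those alternating monthly between two drugs. Set 2 holds everyone else: "patients who are off-cycle of an alternating month on/month off cycle", continuous users and non-users. The SAP concedes that the data do not allow a reliable derivation by program, so "the sponsor will review the inhaled antibiotic usage and will identify the patients to be included in each data set".

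**A contrasting step.** For Cohort 1 hypertonic saline, SAP 8.0 has the Medical Monitor or a designee who "will review all concomitant medications (while blinded to treatment information) prior to database lock". For Cohort 2, hypertonic saline status is entered in the randomization system before randomization.

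**The concern.** A month-on/month-off user scheduled as intended has the baseline measurement at about the end of an off month and the Week 4 measurement at about the end of an on month. The change score then holds any antibiotic effect as well as any study drug effect. With 30 active and 15 placebo subjects, the share of such starters can differ between arms by chance, and a reader of the Cohort 2 result will want to know whether it did and whether it mattered.

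The planned analysis answers poorly, for two reasons. The sets are defined by whether a new cycle begins, not by whether antibiotic exposure changes between the two measurements. They are also filled by judgement, and the SAP does not say that the judgement is made blind to treatment or closed before lock. A subgroup built by hand, with no rule or deadline, carries little weight whichever way it comes out.

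**Working it through.** **1. The plan's own figure.** The inputs are in Protocol 13.2: Cohort 2 has 30 active and 15 placebo subjects (45 split 2:1), tested one-sided at 0.10 with an SD of 7.58. The claim is that "The sample size of 45 subjects will provide 88% to 97% power to detect a difference range of 6% to 8" (in ppFEV1 points).
- SE of the difference = 7.58 × √(1/15 + 1/30) = 2.40 points.
- Noncentral t on 43 degrees of freedom, one-sided 0.10: power 88.4% at 6 points and 97.8% at 8 points. The stated 88% and 97% are reproduced.

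**2. What each set contains.** The states below are inferred from the regimens; the documents do not tabulate them.

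| Regimen | Before Day 1 | At Week 4 | SAP set |
|---|---|---|---|
| Month on/off, on month starting | off | on | 1 |
| Alternating two drugs | on | on | 1 |
| Month on/off, off month starting | on | off | 2 |
| Continuous | on | on | 2 |
| None | off | off | 2 |

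Each set combines subjects whose exposure changes with subjects whose exposure does not.

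**3. Size of a chance shift.** The documents give neither the antibiotic effect nor the share of starters. Assume a drift A of 2 to 5 ppFEV1 points (starters against others) and a starter share p of 30% to 50%.
- SD of the shift = A × √(p(1−p)(1/30 + 1/15)).
- Low end: 2 × √(0.21 × 0.1) = 0.29 points. High end: 5 × √(0.25 × 0.1) = 0.79 points.
- Relative to the SE: 0.29/2.40 = 0.12 and 0.79/2.40 = 0.33.
- Share of outcome variance = A²p(1−p)/7.58²: 4 × 0.21/57.46 = 1.5% and 25 × 0.25/57.46 = 10.9%.

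SAP 6.1 takes the SD of 7.58 from Cohort 1, which was scheduled to the antibiotic cycle in the same way. This variance is therefore already inside the planning SD and the stated power.

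**4. A visible imbalance.** From binomial counts in arms of 30 and 15, the chance that the starter shares differ by 20 percentage points or more, in either direction, is 21% at p = 0.3 and 25% at p = 0.5. Such a difference moves the estimate by 0.2 × A = 0.4 to 1.0 points, or 0.17 to 0.42 SE. If it favours active, the one-sided error conditional on that imbalance rises from 0.10 to about 0.13 to 0.19.

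**5. Precision of the separate subgroups.** If Set 1 holds 30% of subjects (9 active, 4.5 placebo on average), its SE is 7.58 × √(1/9 + 1/4.5) = 4.38. At 50% (15 and 7.5) it is 7.58 × √(1/15 + 1/7.5) = 3.39. Both compare with 2.40 for the whole cohort.

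**6. Would a term in the primary model help?** The Cohort 2 ANCOVA was simulated with and without a starter term (30:15, total SD 7.58, true difference 6, one-sided 0.10). At a 2-point drift the term slightly lowers power, from about 88.0% to 87.8%, because at N = 45 its chance correlation with treatment costs more than it saves. At a 5-point drift it gains 1.4 to 2.3 percentage points.

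**The case against.** Much can be said for the plan as written.

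- **The design already controls phase.** Stable prior antibiotic use is required and cyclic users enter at a common point in both arms. Randomization makes the expected bias zero. This stands. A reader might infer that the primary comparison is confounded or that its model must be changed. The documents do not support that: the drift and starter share are assumptions, the variance is already in the planning SD, and a primary-model term loses power at one end of the assumed range.
- **The sets match their stated question**, which is whether a new cycle starts with study drug, and alternators do start one. Each set compares active with placebo, so starter imbalance is partly addressed. This also stands. What they cannot do is isolate the off-to-on group, and the subgroups are small.
- **The sponsor is blinded** under Protocol 9.5.4. A reader might infer that the lists will be drawn up after unblinding. No passage says so. The general blind ends at unblinding, however, and nothing requires these lists to be final by then.
- **The explicit blinded review in SAP 8.0 is for Cohort 1 only.** Correct. It still serves as a model for a hand classification.
- **Off-cycle subjects need not contradict Protocol 9.5.7.** Set 2 must take every ITT subject not in Set 1, including deviations. That is a fair reading, but the SAP does not state it.

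**Conclusion.** The concern holds for the supportive antibiotic analysis in SAP 12.6.4, not for the validity of the primary test. The analysis depends on hand assignment without a written rule, blinding or a deadline, and its groups cannot cleanly show whether an imbalance in off-to-on starters moved the Cohort 2 estimate. The likely movement is modest: about 0.12 to 0.33 of the standard error, under the assumed drift and starter share. That drift differs by transition is itself an inference from the regimens. The gaps in blinding and grouping do not depend on these assumptions and would remain if the antibiotic effect were small.

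**What to change.** 1. **Classify by direction of change.** In SAP 12.6.4, assign each Cohort 2 subject from antibiotic dates, by a written rule, to off-to-on, no net change (none, continuous, or alternating two drugs) or on-to-off. Protocol 9.5.7 already requires administration dates in the eCRF. The rule should say how unclear dates are handled. SAP 8.0 replaces a start date with a missing day in the first-dose month by the first-dose date, which would turn such a record into a Day 1 start. Any manual review should be blinded to treatment and final before database lock, as for Cohort 1 hypertonic saline.
2. **Keep the primary ANCOVA unchanged.** Add one prespecified supportive ANCOVA of Cohort 2 change in ppFEV1 at Week 4 with this classification as a covariate, in place of reliance on two small separate subgroup tests.
3. **Reconcile the off-cycle category** in SAP 12.6.4 with the 3-day rule in Protocol 9.5.7, for example by stating that it captures protocol deviations.

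The cost is SAP wording, a little blinded review, and one or two model degrees of freedom in a supportive analysis. No new data field is needed.
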